The main content of the document is aimed at describing the design of the validation, where the design of the trial protocol is specified as well as the management plan and the statistical analysis plan. Besides, the patient information sheet and the informed consent are included as part of the ethical approval of the validation for both scenarios.

In particular, for the clinical scenario, two additional sections are described: the regulatory application of the FriWalk and the insurance for the trials.

ACANTO

2 Introduction

ACANTO is a research project aimed to increase the number of older adults who engage in a regular and sustained physical activity. This result is sought by developing a robotic friend that supports the execution of everyday activities that entail a controlled physical effort in public spaces and an intelligent system that produces activity recommendation considering the habit and the preference of the user observed through the robot. Main and specific objectives of the project are detailed below:

- Development of a robotic friend (FriWalk). The FriWalk will offer direct support to the user activities and collect analytics on her/his behaviours.
- Development of a recommendation system for user activities. The recommendation system will rely on a social network created using physical information for users' profilse (the CPSN)
- Development of a cloud of supporting service in the environment. Most of the ability of the FriWalk to offer advanced functionalities in spite of its low cost lies in its reliance to external services that augment its sensing range and its computation abilities

The aim of the pilots conducted in ACANTO project is to evaluate the clinical validity of the robotic system for rehabilitation and diagnostic tool, and assess its impact in enhancing social inclusion of the older population that benefit of using a walker.

In particular, the clinical pilot pursues the following primary goals:

- Mitigate functional deterioration while hospitalization, by performing physical exercise with the FriWalk.
- Recover functional performance earlier after hospitalization.
- Validate FriWalk as a tool for measuring SPPB and gait speed (6m).

For those purposes, a clinical validation plan is stablished which comprises a set of phases detailed in section 3.1.1.3. In case of validation the FriWalk as a therapeutic tool, the patients' selection will be made within 48 hours of initial hospital admission in the Geriatric Acute Care Unit, and in the Orthogeriatrics. Next the participants will sign the inform consent and later they will be assigned by using a randomization process to the control group or to the intervention group. Patients in the intervention group, who are hospitalized in Geriatric Acute Care or in Orthogeriatrics Unit, will dispose of the FriWalk to perform the prescribed rehabilitation exercises. For both groups, data will be collected in five different moments; at patients' admission, at discharge, one month, three and six months after discharge. Regarding the validation as a diagnostic tool, the selected patients will be those who were previously selected for therapeutic validation in Acute Care Geriatrics Unit. Patients will have to perform the Short Physical Performance Battery (SPPB) and the gait speed (6 meters). Then, we will compare data acquired by FriWalk and data acquired by a traditional method.

On the other hand, the social pilot is intended to increase both (1) *social involvement* and (2) *physical activity* of the users. To achieve these targets, a pair of use cases is defined respectively: one by using the social network, and other by using the FriWalk. Therefore, several variables will be measured: performance expectancy, effort expectancy, attitude towards the system, social influence, facilitating conditions, self-efficacy, anxiety, intention to use the system, perceived and actual social involvement, number of steps taken, well-being, perceived sleep quality, fear of falling.

3 Design of the experimental validation 3.1 Clinical trial

3.1.1 Design of the trial protocol

3.1.1.1 Objectives

Primary endpoints:

- Mitigate functional deterioration while hospitalization, by performing physical exercise with the FriWalk.
- Recover functional performance earlier after hospitalization.
- Validate FriWalk as a tool for measuring SPPB and gait speed (6m).

Secondary endpoints:

- To increase physical activity during hospitalization in Geriatric Acute Care and Orthogeriatric Units.
- Evaluate the influence of FriWalk in the onset of delirium during hospitalization.
- Evaluate the influence of FriWalk in the cognitive performance of the patients.
- Evaluate the influence of FriWalk in the affective sphere of the patients.
- Evaluate the influence of FriWalk in the quality of life of the patients.
- Evaluate the influence of FriWalk in the number of falls after discharge.
- Evaluate the influence of FriWalk in mortality.
- Evaluate the influence of FriWalk in the consumption of health resources after discharge.
- Evaluate FriWalk in terms of usability, satisfaction and acceptability.

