3.1.1.3 Protocol

This is a prospective, randomized and blind pilot study.

The FriWalk validation as a therapeutic tool will be carried out in two clinical scenarios, one of them in geriatric acute care and the other in Orthogeriatrics Unit, because people usually use the walker in these units. On the other hand, the FriWalk validation as a diagnostic tool (SPPB and gait speed) will be carried out in Acute Care Geriatrics Unit, in those patients who have been recruited to FriWalk validation as a therapeutic tool.

The duration of the pilot will be one year, we will have two FriWalk during pilot. Recruitment time will be six months from the start of the pilot study.

Regarding the number of patients who will participate in the study, as FriWalk is a new technologic tool, which going to be included in model care in elderly people, we do not have previous data to evaluate the effect of the walker in clinical scenario. Hence, correct sample size cannot be calculated. So, we propose developing a pilot study in which all patients who meet inclusion and exclusion criteria and sign the inform consent will be included. The pilot study will last a year.

Patients' evaluations, in therapeutic tool scenario, will be carried out during hospitalization (in admission and discharge), one month after discharge, three months after discharge and six months after discharge. The last evaluation will be done by phone. A block randomization will be performed to ensure a balance between the control group and the intervention group in each setting. The block size is 4 (2 for control group and 2 for intervention group). In order to perform the randomization, we will always need that one of the FriWalk is free.

In the FriWalk validation as a diagnostic tool, the tests will be performed once there will not be a further follow-up.

In table 1 we will find described the professionals that participate in the pilot study as well as their responsibilities.

Table 1. Professionals.

PROFESSIONALS.		
RESPONSABLE:	COMPETENCES:	
Clinical researcher.	 Pre-screening and screening phases: check that patients meet inclusion and exclusion criteria. Give information to patients and caregivers about the pilot study and provide informed consent. The clinical researcher will carry out the evaluations during hospitalization, in discharge, and afterwards (one month after discharge and three months after discharge). Validation of the FriWalk as a diagnostic tool. 	

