Physician.	 Pre-screening phase: the physician along with the clinical researcher will made a pre- selection of patients that could be participants in the pilot study. 	
Technical support.	- The technical support will develop training sessions about walker use. In addition, the walker maintenance will be carried out.	
Occupational Therapist.	 Exercises prescription. Validation of the FriWalk as diagnostic tool in Geriatrics Acute Care Unit. 	
FIB-HUG Professionals.	- They will perform the analysis data.	

A. VALIDATION OF THE FRIWALK AS A THERAPEUTIC TOOL:

Patients' selection will be made within 48 hours of initial hospital admission in the Geriatric Acute Care Unit, and in the Orthogeriatrics Unit after the stand permission by traumatology. These patients will be identified in both units through the admission list. Then physician and clinical researcher will check those participants who fulfil the inclusion and exclusion criteria. Next the participants will sign the informed consent and later the will be assigned by using a randomization process (through the www.randomizerd.org tool) to the control group or to the intervention group.

- **Control group**: the participants will receive the usual intervention, including rehabilitation programs if the participants need it during hospitalization.
- Intervention group: the participants will receive the usual intervention, including rehabilitation programs if the participants need it. In addition, we will provide them with the FriWalk as well as the exercises recommendations which prescribed by their physician and the Occupational Therapist.

Patients in the intervention group, who are hospitalized in Geriatric Acute Care or in Orthogeriatrics Unit, will dispose of the FriWalk at the time they have received authorization for walking by their doctor in Acute Care Unit, or for standing in Orthogeriatrics Unit until their discharge respectively.

The evaluations will be the same in both groups. When clinical researcher detects any alterations in the tests or questionnaires which might condition the patient's clinical management, the physician will be informed to take the appropriate measurements.

For both groups, data will be collected in five different moments; when patients' admission, at discharge, one month, three and six months after discharge.

In table 2 is describe pilot study in Geriatric Acute Care Unit and Orthogeriatrics Unit.

PHASE I: PRE-SCREENING.		
RESPONSABLE:	DESCRIPTION:	

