Clinical researcher.	 New evaluation will be carried out at discharge moment with different tests and evaluations from admission. Demographic and clinical data. Gait speed (6 meters). SPPB (Short Physical Performance Battery). Barthel Índex. Lawton and Brody. Confusion Assessment Method. Semantic and Phonologic fluency. MMSE. Clock Drawing Test. Yesavage. EuroQL-5D. Visual Analogue Scale for pain (only in Orthogeriatric Unit). Length of admission. Adherence to treatment. We obtain this information by the FriWalk in the intervention group, and by questionnaires in the control group. Assistant level at discharge. System _Usability Test (intervention group).
PHASE VIII: VISIT 1 MC	ONTH AFTER DISCHARGE.
RESPONSABLE:	DESCRIPTION:
Clinical researcher.	 New evaluation will be carried out one month after discharge. Different test will be performed. Demographic and clinical data. Gait speed (6 meters). SPPB (Short Physical Performance Battery).

	/
	 Barthel Índex. Lawton and Brody. Confusion Assessment Method. Semantic and Phonologic fluency. MMSE. Clock Drawing Test. Yesavage.
	 EuroQL-5D. Visual Analogue Scale for pain (only in Orthogeriatric Unit). New admissions. Emergency visits.
	 Admission days in Emergency. Primary care visits Falls. Mortality. Assistance level at month 1.
PHASE IX: VISIT 3 MONT	
RESPONSABLE:	DESCRIPTION:
Clinical researcher.	 Last evaluation will be carried out. Demographic and clinical data. Gait speed (6 meters). SPPB (Short Physical Performance Battery). Barthel Índex. Lawton and Brody. Confusion Assessment Method. Semantic and Phonologic fluency. MMSE. Clock Drawing Test. Yesavage. EuroQL-5D. Visual Analogue Scale for pain (only in Orthogeriatric Unit). New admissions. Emergency visits. Admission days in Emergency. Primary care visits Falls. Mortality. Assistance level at month 1.
PHASE X: TELEPHON EVALUATIO	
RESPONSABLE:	DESCRIPTION:
Clinical researcher.	 We will make a call, 6 months after discharge: Barthel Índex. EuroQL. Mortality. Assistance level at month 1.
PHASE XI: DA	TA ANALYSIS.
RESPONSABLE:	DESCRIPTION:
FIB-HUG professionals.	At the end of the study, data analysis will be carried out using the information stored during the pilot study. Then, conclusions will be drawn about the use of the walker.

B. VALIDATION OF THE FRIWALK AS A DIAGNOSTIC TOOL.

Patients selected to validate the FriWalk as a diagnostic tool will be those who have been selected for therapeutic validation in Acute Care Geriatrics Unit setting.

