3	The FriWalk breaks down during the development of the trial	Unlikely	Significant	There will be a minimum of 2 FriWalks in the clinical dependencies during the clinical study. If one breaks down, the local technical team will try to fix it with remote support from the walker developers; in case it is not possible, and depending on the actual damage, technology specialist will come to the site to restore the walker into operation.
4	A patient gets injured while using FriWalk	Unlikely	Major	Although it is very unlikely, a patient can fall down and get injured while using FriWalk. In that case, as the study will be carried out within Hospital dependencies, the patient will receive immediate clinical assistance. The insurance will economically cover with the expenses.

Table 4. Risk Action Plan.

5	The number of participants is not enough to guarantee strong scientific results	Possible	Major	A weekly estimation of participants recruited will be set. If the number of participants is not achieved, the recruitment activities will be reinforced. If a severe deviation occurs, an extension of the study lifetime will be requested
6	Problems related to the consortium communication during the study	Unlikely	Significant	Potentiate team building among members and increase face to face or teleconference communications when possible. Gather all points of view and intervention of the project coordinator to solve the problem in case it is needed
7	Problems in the management of the project	Possible	Significant	A close follow up of project activities will be carried out. Periodic meetings and reports are scheduled
8	Problems in the dissemination of results	Possible	Significant	The dissemination activities will be planned from the onset of the clinical study. Periodic reviews are scheduled

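### Delirium onset during the stay is tested only at admission and discharge, so episodes that start and clear in between are not recorded

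*Protocol*

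**What the plan says.** Section 3.1.1.1 lists nine secondary aims. One is to "Evaluate the influence of FriWalk in the onset of delirium during hospitalization", so the endpoint is new delirium and its window is the whole stay.

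Section 3.1.1.3 fixes when patients are assessed. Evaluations "will be carried out during hospitalization (in admission and discharge", followed by the contacts after discharge. Part A of the same section repeats that "data will be collected in five different moments; when patients' admission, at discharge, one month, three and six months after discharge".

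Table 2 puts the Confusion Assessment Method in the first-visit list (Phase IV) and again at discharge (Phase VII) and at one and three months. Phase VII is introduced with the words "New evaluation will be carried out at discharge moment with different tests and evaluations from admission", but its list repeats this test. Phase VI, between admission and discharge, provides technical help and clinical follow-up and lists no delirium test. Table 5 (section 3.1.3.1) describes the instrument as a set of yes/no questions and states no repeat or look-back interval.

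Patients in the intervention group have the FriWalk from the time they are authorised to walk (Acute Care) or, in the protocol's words, "for standing in Orthogeriatrics Unit until their discharge respectively". All therapeutic use of the device therefore falls between the two in-hospital tests.

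**The concern.** Onset over an interval cannot be read from two spot tests at its ends unless every new episode lasts until the second test. Delirium can resolve within days, and a patient who is negative at admission, delirious mid-stay and negative at discharge is recorded as never having had it.

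Two things are at stake. First, events are lost in a pilot that has no calculated sample size, two devices and six months of recruitment. Second, the quantity compared changes. Delirium present at discharge depends on how often episodes start, how long they last and how long the stay is. An arm difference could then reflect duration or length of stay rather than onset. A SAP could define the analysis set, but it could not supply observations that the protocol does not schedule.

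**Working it through.** **Window against schedule.** The protocol has no delirium figure to reproduce, so the main check compares the endpoint's window with the assessment lists.

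| Part of the stay | Delirium assessment listed | What it shows |
|---|---|---|
| Admission (Phase IV) | Confusion Assessment Method | Delirium already present |
| Stay, including device use (Phase VI) | None | Nothing |
| Discharge (Phase VII) | Confusion Assessment Method | Delirium still present |

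An episode confined to the middle row has no named place on any form.

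**Illustration of the loss.** Assumptions, none of them from the protocol: onset is uniform over a stay of L days, episode duration is exponential with mean D days, and the test has no error. The share of new episodes still present at discharge is

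share = (D/L) × (1 − exp(−L/D)).

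For L = 7 and D = 2: (2/7) × (1 − exp(−3.5)) = 0.286 × 0.970 = 0.28.

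| L (days) | D = 1 | D = 2 | D = 3 | D = 5 |
|---|---|---|---|---|
| 5 | 0.20 | 0.37 | 0.49 | 0.63 |
| 7 | 0.14 | 0.28 | 0.39 | 0.54 |
| 10 | 0.10 | 0.20 | 0.29 | 0.43 |
| 14 | 0.07 | 0.14 | 0.21 | 0.34 |

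The range is 7% to 63%.

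**Mixing of onset and duration.** With L = 7 and the same incidence in both arms, mean durations of 2 and 3 days give shares of 0.28 and 0.39. The ratio at discharge is 0.28/0.39 = 0.72, although onset does not differ at all.

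**What lost events cost.** Assume a true incidence of 30% v 15%, two-sided 0.05 (the protocol states 0.05 without sidedness), 80% power, and the same share found in each arm. Then

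n per arm = [1.960 × √(2p̄(1 − p̄)) + 0.842 × √(p₁(1 − p₁) + p₂(1 − p₂))]² / (p₁ − p₂)².

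With full capture, p̄ = 0.225 and n = (1.1575 + 0.4889)² / 0.0225 = 120.5, so 121. Multiplying both rates by the share found gives:

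| Share found | Observed rates | n per arm |
|---|---|---|
| 100% | 30% v 15% | 121 |
| 63% | 18.9% v 9.45% | 213 |
| 28% | 8.4% v 4.2% | 525 |
| 7% | 2.1% v 1.05% | 2207 |

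These sizes show only the direction and steepness of the loss. The protocol plans no such comparison.

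**The case against.** The strongest reply is that delirium is one of nine secondary aims in a pilot, that the two tests do record something, and that physicians follow patients throughout the stay. The discharge list also has an unspecified entry for clinical data, where an episode could be noted. All of this is true. It limits the weight of the point but does not remove it, because nothing says that delirium during the stay is to be looked for or entered. The rates and durations above are also assumptions, so the loss could be modest.

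A reader might infer more than the documents support:

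- *That delirium is not captured at all, or that cases present at admission cannot be separated from new ones.* The discharge test finds episodes still present, and the admission test identifies prevalent cases.
- *That the falls endpoint misses the period of device use.* Its wording is to "Evaluate the influence of FriWalk in the number of falls after discharge", and falls are listed at one and three months. Leaving out in-hospital falls is its stated scope. Table 4 does accept that "a patient can fall down and get injured while using FriWalk", and rates this unlikely but major. The stated route for such events is adverse event reporting to the ethics committee (section 3.1.2, item r).
- *That mortality is conditional on leaving hospital alive.* The aim, "Evaluate the influence of FriWalk in mortality", has no time window. Mortality is listed at one, three and six months, and an in-hospital death can still be counted then. What is missing is a discharge item and a stated time origin.

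**Conclusion.** The point holds for delirium. The endpoint is onset during the stay, but the schedule yields delirium present at admission and at discharge, and episodes that begin and end between the two tests are missed. This follows from the protocol's own text and needs no assumption beyond some episodes being shorter than the remaining stay.

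How many are missed cannot be determined from the protocol. The range of 7% to 63% found rests entirely on the assumed stays, mean durations, uniform onset and error-free testing. The point should be corrected, but as a matter affecting one secondary endpoint. It does not threaten the primary aims. It does not extend to falls, and for deaths it amounts to a minor omission on one form.

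**What to change.** Add one item to the Phase VII discharge form, completed identically in both arms: a review of the ward record for any delirium episode, with its date, between randomisation and discharge. Keep the scheduled Confusion Assessment Method result as a separate component. Analyse incident delirium among patients negative at admission. Table 2 places that test before training on the device, so the restriction does not condition on anything the device could have changed.

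The cost is a few minutes of record abstraction per patient by existing staff. There are two drawbacks. Ward records are less sensitive than repeated testing, and ward staff can see who has the walker, so recording may differ by arm. The scheduled-test result should therefore be reported alongside. Repeated in-stay testing on the same timetable in both arms would be stronger, at the cost of more assessor time.

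If neither is done, rename the endpoint *delirium present at discharge among patients negative at admission*.

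As a minor addition, put a mortality item on the same form and count deaths from randomisation. Recording in-hospital falls by arm on that form is an optional safety addition and does not correct an error.

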3.1.1.2 Participants

The FriWalk validation as a therapeutic tool will be carried out in two different and independent clinical scenarios (two settings), one of them will be Geriatric Acute Care Unit and the other will be Orthogeriatrics Unit. We will select patients over 75 years old in both scenarios. For the validation of the FriWalk as a diagnostic tool, we will recruit patients over 75 years old only in Geriatric Acute Care Unit.

As it is a novel technological tool in the care model of elderly patients, we do not have previous data to evaluate the effect of an intelligent walker in the clinical scenarios. Therefore, we will develop a pilot in which we will include all patients who meet the eligibility criteria and sign the informed consent for a stipulated time of one year.

INCLUSION AND EXCLUSION CRITERIA:

A. GERIATRIC ACUTE CARE UNIT:

- Inclusion criteria:
 - \circ Patients' \geq 75 years old.
 - Supervision during hospitalization by caregivers or family.
 - Ability to walk with or without aid prior to hospitalization.
- Exclusion criteria:
 - $\circ \quad \geq 48h \text{ of stay in the hospital.}$
 - $\circ \quad \mbox{Inability to understand and use the FriWalk}.$
 - o Illness that impedes carrying out the prescribed therapy.

- Acute myocardial infarction in the last 3 months.
- Instable cardiovascular disease.
- Terminal illness.
- Other pathologies involving clinical instability.
- Functional impairment established (Barthel Index < 40).
- Precedent of alcohol and/or drug abuse.
- Psychiatric disorders (Schizophrenia and psychotics disorders.
- Participation in any other clinical study.

B. ORTHOGERIATRICS UNIT:

Inclusion criteria:

0

- Patients' \geq 75 years old.
- Hip fracture surgery with permission to stand during hospitalisation.
- Supervision during hospitalization by caregivers or family.
- Ability to walk with or without aid prior to hospitalization.
- Exclusion criteria:
 - $\circ \geq 48h$ after surgery intervention.
 - Inability to understand and use the FriWalk.
 - Illness that impedes carrying out the prescribed therapy.
 - Acute myocardial infarction in the last 3 months.
 - Instable cardiovascular disease.
 - Terminal illness.
 - Other pathologies involving clinical instability.
 - \circ Functional impairment established (Barthel Index < 40).
 - History of alcohol and/or drug abuse.
 - Psychiatric disorders (Schizophrenia and psychotics disorders.
 - Participation in any other clinical study.

